Apolipoprotein E (*ApoE*) and *NAT2* genotyping/phenotyping will be conducted. *ApoE4* homozygous or heterozygous status versus non-carriers and *NAT2* status will be used in the statistical analysis to determine the effects on treatment response and safety. Remaining genomic DNA may also be stored for up to 15 years to be used to examine the role of DNA sequence variability on the absorption, distribution, metabolism, and elimination of E2609, development of AEs, as well as the underlying AD. Variations in E2609 exposure or the occurrence of AEs observed in the study population may be evaluated by correlation of single-nucleotide polymorphisms with PK, safety, or PD data.

Safety Assessments

Every effort should be made to keep the site staff responsible for reviewing laboratory reports and assessing AEs separate from the site staff responsible for the efficacy assessments, particularly for the CDR. (revised per Amendment 01) Routine safety assessments will include the monitoring and recording all AEs and SAEs, monitoring of hematology, blood chemistry, and urinalysis, measurement of vital signs, regular ECGs, physical and neurological examinations, and centralized dermatological assessments (via photography) at regular intervals. AEs that might indicate signals of possible drug abuse potential will require a more detailed follow-up. Subjects reporting AEs relating to abnormal dreams, nightmares, or sleep terror will be questioned on the frequency and impact of these events.

Complete blood counts and lymphocyte subset absolute counts and percentages will be measured (by a centralized laboratory) every week for the first month, every 2 weeks for the next 2 months (Months 2 and 3) and monthly for the next 3 months (Months 4, 5, and 6). Thereafter they will be monitored every 3 months until the end of the Treatment Period and at both Follow-Up Visits. Serum IgG, IgA, and IgM will be monitored monthly for the first 3 months, at 6, 12, and 18 months, and at both Follow-Up Visits.

Peripheral blood mononuclear cells (PBMCs) will be collected at Baseline, during treatment, and posttreatment for exploratory immunomodulatory and immune-based analyses.

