9.5.1.5.3 LABORATORY MEASUREMENTS

Clinical laboratory tests to be performed, including hematology, chemistry, urinalysis, and CSF are summarized in Table 4. Subjects should be in a seated or supine position during blood collection. Table 6 and Table 7 show the visits and time points at which blood for clinical laboratory tests and urine for urinalysis will be collected in the study.

See Section 9.3.3 for safety criteria for discontinuation from study drug related to absolute counts of CD4, CD8, and B lymphocytes, and for lymphocyte subset counts.

Table 4 Clinical Laboratory Tests

| Category | Parameters |
|-----------------------------|---|
| Hematology | Hematocrit, hemoglobin, platelets, red blood cell count, and white blood cell count with differential (bands, basophils, eosinophils, lymphocytes, monocytes, neutrophils), and (Screening and Baseline only), PT, PTT, and INR |
| Chemistry | |
| Electrolytes | Bicarbonate, calcium, chloride, phosphate, potassium, sodium |
| Liver function tests | Alanine aminotransferase, alkaline phosphatase, aspartate aminotransferase, gamma glutamyl transpeptidase, direct bilirubin, total bilirubin |
| Renal function tests | Blood urea/blood urea nitrogen, creatinine |
| Other | Albumin, cholesterol, globulin, glucose, lactate dehydrogenase, total protein, triglycerides, uric acid |
| Urinalysis | Bacteria, casts, crystals, epithelial cells, glucose, ketones, occult blood, pH, protein, red blood cells, specific gravity, white blood cells |
| Other | Lymphocyte subset analyses (see Table 5). Regulatory T cells will be measured using CD4, CD25, and CD127 cell surface markers and FoxP3 intracellular marker. PBMCs Ig analyses (IgG, IgA, and IgM). Viral screen (HCVAb [Hepatitis C] and HBsAg [Hepatitis B]). Viral characterization (including HSV1, HSV2 and CMV, etc) Serum pregnancy test (females of child bearing potential only) Tuberculosis Interferon Gamma Release Assays Tests for thyroid function (thyroid stimulating hormone, free triiodothyronine and free thyroxine) and vitamin B12 Blood sample for storage for subsequent testing of immune status Cerebrospinal fluid sampling |

CMV = cytomegalovirus, HBsAg = hepatitis B surface antigen, HCVAb = hepatitis C virus antibody, HSV = herpes simplex virus, Ig = immunoglobulin, INR = International Normalized Ratio, PBMC = peripheral blood mononuclear cell, PT = prothrombin time, PTT = partial thromboplastin time.

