| Nominal months elapsed since first dose | 0 | | | | 1 | | 2 | | 3 | 4 | 5 | 6 | 9 | 12 | 15 | 18 | | 19 | 21 | | |
| Procedures/ Assessments | | | | | | | | | | | | | | | | | | | | | |
| Routine physical examination | X | | | | X | | X | | X | | | X | X | X | X | X | X | X | X ^e | X | |
| Inclusion and Exclusion criteria | X | | | | | | | | | | | | | | | | | | | | |
| Vital signs ^f | X | X | X | X | X | X | X | X | X | X | X | X | X | X | X | X | X | X | X ^e | X | |
| Respiratory rate | | | | | X | | X | | X | X | X | X | X | X | X | X | X | X | X ^e | X | |
| Weight | | | | | | | | | X | | | X | X | X | X | X | X | | X | X | |
| Centralized dermatological assessment via photography ^g | | | | | | | | | X | | | X | X | X | X | X | X | | X | X | |
| Neurological examination ^h | | | | | | | | | | | | X | | X | | X | X | X | X | X | |
| Ophthalmic examination ⁱ | | | | | | | | | | | | | | | | | | | | X | |
| Concomitant medications ^j | | X | X | X | X | X | X | X | X | X | X | X | X | X | X | X | X | X | X | X | |
| 12-lead ECG ^k | | | X | | X | | X | | X | | | X | | X | | X | X | X | X ^e | X | |
| Clinical biochemistry and urinalysis | | | X | | X | | X | | X | | | X | X | X | X | X | X | X | X ^e | X | |
| Complete blood count | | X | X | X | X | X | X | X | X | X | X | X | X | X | X | X | X | X | X ^e | X | |
| Blood samples for lymphocyte subset analyses ^l | | X | X | X | X | X | X | X | X | X | X | X | X | X | X | X | X | X | X ^e | X | |
| Blood samples for Igs ^m | | | | | X | | X | | X | | | X | | X | | X | X | X | X ^e | X | |
| Blood samples for isolation of PBMCs | | | X | | | | | | X | | | | | | | | | | X | | |
| Urine pregnancy test (females of CBP only) | X ⁿ | | | | | | | | X | | | X | X | X | X | X | X | X | | X | |
| Blood sample for storage for immune status ^o | | | | | X | | | | X | | | X | | X | | X | X | X | X | X | |
| CBB and ISLT ^p | | | | | | | | | X | | | X | X | X | X | X | X | X | X | | |
| MMSE ^p | | | | | | | | | X | | | X | X | X | X | X | X | X | X | | |
| CDR ^p | | | | | | | | | X | | | X | X | X | X | X | X | X | X | | |
| ADAS-cog ₁₄ ^p | | | | | | | | | X | | | X | X | X | X | X | X | X | X | | |

Table 7 Schedule of Procedures/Assessments in Study 202: Randomization Phase (Visit 3 through Visit 20)

| Phase | Randomization | | | | | | | | | | | | | | | | | | | UNS Visit ^d |

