- c: All subjects, regardless of whether they complete all 18 months of treatment or discontinue study drug prematurely, will complete 2 posttreatment Follow-Up visits; one 4 weeks after the last dose of study drug and a second 12 weeks after the last dose of study drug (Visit 19 and Visit 20 respectively). If clinically indicated, more frequent safety assessments can be made as UNS assessments or visits during the posttreatment Follow-Up period.
- d: Unscheduled visits may be conducted at any time that safety or safety MRI data indicate per protocol or as clinically indicated in the judgment of the investigator. Note that not all assessments indicated under UNS Visits need be conducted – actual assessments needed will be determined by the investigator and will be based on the specific visit needs.
- e: Only if clinically significant abnormalities are found at Visit 19 and the investigator considers it necessary to repeat at Visit 20. However, lymphocyte subsets and Igs should be repeated at Visit 20 if they were outside of the normal range (regardless of clinical significance) at Visit 19.
- f: Measurements of body temperature and sitting blood pressure and heart rate will be obtained.
- g: Centralized skin assessments using standardized photography will be conducted by a reviewing dermatologist. These assessments will specifically include evaluation of any areas of depigmentation or any rash. Additional UNS dermatological assessments should be conducted in response to any dermatological AEs of concern, eg, depigmentation, rash, herpetic lesion.
- h: Examples of neurological signs that may indicate new central nervous system pathology that may need further investigation include (but not limited to) visual disturbance, dysarthria, dysphasia, muscle strength, limb weakness, hyperflexia, paraparesis, micturition difficulty or urgency or incontinence, ataxia, neuropsychiatric or cognitive decline in excess of expectations based on the subject's recent history.
- i: If the subject experiences visual disturbances during the course of the study, the subject will be referred to a specialist for a further ophthalmic examination, which should include fundoscopy to look at the optic disc, macula and the rest of the retina as well as an assessment of visual acuity and visual fields
- j: Please refer to [Section 9.4.7](#), which details prohibited and permitted medications in the study and associated timeframes.

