9.5.2.2 Description of Procedures/Assessments Schedule

Please refer to [Table 6](#) and [Table 7](#) for the timings of the procedures and assessments to be performed during the study. Screening assessments will be organized into 4 tiers (see [Table 6](#), [Section 9.1.1.1](#), and [Figure 2](#)).

See [Section 9.5.1](#) for a full description of the procedures and assessments to be performed during this study.

[Table 8](#) presents the number of blood and CSF samples, and the total volume of blood and CSF that will be collected throughout the study. Additional samples may be taken at the discretion of the investigator if the results of any tests fall outside reference ranges or if clinical symptoms necessitate testing to ensure subject safety.

Table 8 Summary of Blood and CSF Sample Volumes

| Assessment | Total number of collection time points | Number of time points x volume per collection (mL whole blood or CSF) | | Total volume (mL whole blood or CSF) |
|--|--|---|---------------------------------|--------------------------------------|
| | | Screening and Baseline Periods | Treatment and Follow-Up Periods | |
| Blood | | | | |
| Chemistry | 12 | 2 x 2 mL | 10 x 2 mL | 24 mL |
| Hematology | 18 | 2 x 5 mL | 16 x 5 mL | 90 mL |
| Lymphocyte subset analyses | 18 | 2 x 4 mL | 16 x 4 mL | 72 mL |
| PBMC | 4 | 1 x 16 mL | 3 x 16 mL | 64 mL |
| IgA, IgM, IgG | 9 | 2 x 2 mL | 7 x 2 mL | 18 mL |
| PT, PTT for INR | 2 | 2 x 3 mL | None | 6 mL |
| Thyroid function tests (thyroid stimulating hormone, free triiodothyronine and free thyroxine) | 1 | 1 x 3 mL | None | 3 mL |
| Viral screen (Hepatitis B and C) | 1 | 1 x 4 mL | None | 4 mL |
| Viral characterization | 1 | 1 x 4 mL | None | 4 mL |
| Vitamin B12 | 1 | 1 x 2 mL | None | 2 mL |
| Serum pregnancy test | 1 | 1 x 2 mL | None | 2 mL |
| Tuberculosis (interferon-gamma release assays) | 1 | 1 x 3 mL | None | 3 mL |
| Sample for immune status | 8 | 1 x 4 mL | 7 x 4 mL | 32 mL |
| PD sample | 9 | 1 x 4 mL | 8 x 4 mL | 36 mL |
| PK analysis | 7 | 1 x 3 mL | 6 x 6 mL | 39 mL |
| Pharmacogenetic sample | 1 | 1 x 3 mL | None | 3 mL |
| All blood samples, total volume whole blood collected | | 80 mL | 322 mL | 402 mL |
| CSF | | | | |
| PD and PK samples | 3 | 1 x 12 mL | 2 x 12 mL | 36 mL |

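### Version 3.0 Synopsis sets blood counts, lymphocyte subsets and immunoglobulins at both Follow-Up Visits, Table 7 makes Visit 20 conditional on Visit 19, and Section 9.7.1.8.3 still summarizes Visit 20 by arm (minor)

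*Protocol*

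**What the plan says.** All the texts compared here belong to Version 3.0 (Amendment 01).

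- **Synopsis, Safety Assessments.** For complete blood counts and lymphocyte subsets, after the denser early schedule: "Thereafter they will be monitored every 3 months until the end of the Treatment Period and at both Follow-Up Visits". For the three immunoglobulins: "monitored monthly for the first 3 months, at 6, 12, and 18 months, and at both Follow-Up Visits". Neither sentence carries a condition.
- **Section 9.5.2.1, Table 7.** The three rows have a plain mark at Visit 19 and a mark with note e at Visit 20. The general rule in note e, which governs the blood count, allows a Visit 20 test only if Visit 19 showed a clinically significant abnormality and the investigator thinks a repeat necessary. A second sentence covers the other two tests: "lymphocyte subsets and Igs should be repeated at Visit 20 if they were outside of the normal range" at Visit 19, whatever the clinical significance.
- **Which schedule sites follow.** Section 9.5.1.5.3 says that Tables 6 and 7 "show the visits and time points at which blood for clinical laboratory tests and urine for urinalysis will be collected". Section 9.5.2.2 refers the reader to the same tables "for the timings of the procedures and assessments to be performed during the study".
- **Section 9.5.2.2, Table 8.** It counts draws per test, for example "Lymphocyte subset analyses | 18 | 2 x 4 mL | 16 x 4 mL | 72 mL" and "Sample for immune status | 8 | 1 x 4 mL | 7 x 4 mL | 32 mL".
- **Section 9.7.1.8.3.** Actual values, changes from baseline and low/normal/high shifts are tabulated for each visit after baseline, by treatment group. Lymphocyte subsets and immunoglobulins are handled like other laboratory parameters, and mean lymphocyte subsets are also plotted over time by dose. Visit 20 is not excepted.

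**The concern.** The protocol states two incompatible Visit 20 schedules for the same three tests, and it fixes an analysis that suits only one of them. If sites follow Table 7, the Visit 20 mean, shift percentages and plotted point come from subjects tested because their Visit 19 value was abnormal. They would appear beside visits at which everyone was measured. Arms would not be comparable at Visit 20 either if the share retested differs between them, which is possible for a drug suspected of lowering lymphocytes.

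These parameters matter. Primary objective 2 names immunological and hematological parameters. Section 7.1 reports falls in lymphocyte subsets that resolved after dosing stopped, but Section 7 gives 14 days as the longest dosing so far. Recovery after 18 months of treatment is therefore an open question. A Visit 20 point built from retested subjects could look like failure to recover when it only reflects who was retested.

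**Working it through.** **Step 1. Does Table 8 count Visit 20?** I counted the Table 7 marks after baseline for a subject who completes treatment, leaving out the early-discontinuation and unscheduled columns.

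| Row | Visit 20 mark | Visits counted | Count | Table 8 |
|---|---|---|---|---|
| Blood count | note e | 4 to 19 | 16 | 16 |
| Lymphocyte subsets | note e | 4 to 19 | 16 | 16 |
| Immunoglobulins | note e | 7, 9, 11, 14, 16, 18, 19 | 7 | 7 |
| Chemistry | note e | 5, 7, 9, 11, 14 to 19 | 10 | 10 |
| PBMC | plain | 5, 11, 20 | 3 | 3 |
| Immune status | plain | 7, 11, 14, 16, 18, 19, 20 | 7 | 7 |
| PD sample | plain | 5, 7, 11, 14, 16, 18, 19, 20 | 8 | 8 |

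The note-e rows match only without Visit 20; the plain rows match only with it. One repeated blood row does not fit as extracted: PK shows a plain mark in the Visit 20 column, while Table 8 counts 6 post-baseline time points. Section 9.5.1.4.1 lists PK samples at Visits 5, 7, 11, 14, 16 and 18 (or early discontinuation) and none at Visit 20, so this is probably an unscheduled-visit mark shifted in extraction. PK is not one of the disputed tests.

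**Step 2. Reproduce the volumes.** Row volume = (screening and baseline draws + later draws) × mL per draw.

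- Hematology: (2 + 16) × 5 = 90 mL
- Lymphocyte subsets: (2 + 16) × 4 = 72 mL
- Immunoglobulins: (2 + 7) × 2 = 18 mL

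Treatment and follow-up, in the order chemistry, hematology, subsets, PBMC, immunoglobulins, immune status, PD, PK: 20 + 80 + 64 + 48 + 14 + 28 + 32 + 36 = 322 mL. With 80 mL before treatment, the total is 402 mL. Both equal the stated totals.

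**Step 3. What the Synopsis schedule would give.** One more draw per subject for each test means 17, 17 and 8 post-baseline draws, or 19, 19 and 10 time points in all.

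- Hematology: 19 × 5 = 95 mL
- Lymphocyte subsets: 19 × 4 = 76 mL
- Immunoglobulins: 10 × 2 = 20 mL
- Added volume: 5 + 4 + 2 = 11 mL
- New totals: 322 + 11 = 333 mL and 402 + 11 = 413 mL

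**Step 4. Set the analysis text against the sampling.** Under Table 7, each subject has one guaranteed follow-up value per test, at Visit 19. A Visit 20 value exists only where the Visit 19 result met note e. Section 9.7.1.8.3 bases percentages on subjects with nonmissing baseline and postbaseline results. That sets the denominator to the retested subjects; it does not remove the selection. Two displays are unaffected, because Visit 20 falls after treatment: the end-of-treatment summary (last on-treatment value) and the shift to the highest and lowest value in the treatment period.

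**The case against.** The strongest reply is that the working schedule is clear. Two sections direct sites to Tables 6 and 7, note e is specific with its own rule for subsets and immunoglobulins, and Table 8 agrees. The Synopsis is then a compressed sentence that was never aligned, and the display of conditionally collected values is detail for the SAP, which is not at hand.

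Most of the first part stands. The Synopsis is the outlier, and a reader who infers that sites will not know what to draw goes further than the documents allow. But the Synopsis sentences still promise every subject a measurement that note e withdraws. The second part stands only partly. The point does not rest on absent detail: Section 9.7.1.8.3 itself commits to summaries at every visit after baseline, and the conditional schedule cannot support that for Visit 20.

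It is also fair that keeping Visit 20 values out of the arm summaries is one acceptable display among several. Showing the number tested with a clear label is another. Whichever is used, unresolved abnormalities after treatment must stay visible.

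A reader might extend the contradiction to the other note-e rows, such as "Clinical biochemistry and urinalysis", vital signs other than weight, and ECG. The documents do not support that: the Synopsis does not promise those tests at both Follow-Up Visits. The same labelling could be applied to them, but nothing in their schedule conflicts.

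**Conclusion.** The contradiction is real within Version 3.0. If Table 7 is followed, the Visit 20 summaries of blood counts, lymphocyte subsets and immunoglobulins describe subjects selected on their Visit 19 result. The consequence is minor: the summaries are descriptive, no decision rule uses them, Visit 19 measures everyone still attending, and note e provides for repeating abnormal values. Efficacy conclusions are untouched. A reader might infer that the safety evaluation or the drug-discontinuation rules are compromised; those rules act on treatment with their own retests, so they are not.

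No size of bias is claimed. For illustration, assume standardized normal values, no drug or time effect, and retesting only below the lower limit. The Visit 20 mean of those retested is then −ρ × φ(z)/p, where p is the share retested, z the p-quantile of the standard normal, φ its density and ρ the correlation between the visits. With p from 2.5% to 27% and ρ from 0.5 to 0.9, this lies about 0.6 to 2.1 SD below the true mean. These inputs are assumptions: the protocol gives neither the retested share nor the correlation, note e acts on values out of range in either direction, and blood counts also depend on investigator judgment. What the documents do fix is the sampling difference: one Visit 20 draw per subject per test under the Synopsis, none counted in Table 8.

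Appendix 2, Listing 2, in a later version cites an Amendment 02, whose Synopsis, Table 7 and Section 9.7 are not shown. Whether the point was corrected there cannot be checked.

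**What to change.** Choose one schedule and make the text agree with it.

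1. **Follow the Synopsis.** Remove note e from the blood count, lymphocyte subset and immunoglobulin rows at Visit 20, and update Table 8 with the Step 3 counts and volumes. Section 9.7.1.8.3 then needs no change for these tests. The cost is 11 mL per subject, at a visit that already takes 16 + 4 + 4 = 24 mL (PBMC, immune status, PD) from every subject.
2. **Keep note e.** Correct the two Synopsis sentences so that Visit 20 testing depends on Visit 19. State in Section 9.7.1.8.3 that Visit 20 values of these tests are kept out of the by-visit arm means, shift percentages and plots, and are reported separately as Visit 19 to Visit 20 follow-up of the retested subjects, with their number per arm. This costs wording only.

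Option 1 gives better information on recovery off drug; option 2 is cheaper and removes the misleading last time point. Under either option, the separate reporting may be extended to chemistry, urinalysis, vital signs other than weight, and ECG for consistency.

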9.5.2.2 Description of Procedures/Assessments Schedule

Please refer to [Table 6](#) and [Table 7](#) for the timings of the procedures and assessments to be performed during the study. Screening assessments will be organized into 4 tiers (see [Table 6](#), [Section 9.1.1.1](#), and [Figure 2](#)).

See [Section 9.5.1](#) for a full description of the procedures and assessments to be performed during this study.

[Table 8](#) presents the number of blood and CSF samples, and the total volume of blood and CSF that will be collected throughout the study. Additional samples may be taken at the discretion of the investigator if the results of any tests fall outside reference ranges or if clinical symptoms necessitate testing to ensure subject safety.

Table 8 Summary of Blood and CSF Sample Volumes

| Assessment | Total number of collection time points | Number of time points x volume per collection (mL whole blood or CSF) | | Total volume (mL whole blood or CSF) |
|--|--|---|---------------------------------|--------------------------------------|
| | | Screening and Baseline Periods | Treatment and Follow-Up Periods | |
| Blood | | | | |
| Chemistry | 12 | 2 x 2 mL | 10 x 2 mL | 24 mL |
| Hematology | 18 | 2 x 5 mL | 16 x 5 mL | 90 mL |
| Lymphocyte subset analyses | 18 | 2 x 4 mL | 16 x 4 mL | 72 mL |
| PBMC | 4 | 1 x 16 mL | 3 x 16 mL | 64 mL |
| IgA, IgM, IgG | 9 | 2 x 2 mL | 7 x 2 mL | 18 mL |
| PT, PTT for INR | 2 | 2 x 3 mL | None | 6 mL |
| Thyroid function tests (thyroid stimulating hormone, free triiodothyronine and free thyroxine) | 1 | 1 x 3 mL | None | 3 mL |
| Viral screen (Hepatitis B and C) | 1 | 1 x 4 mL | None | 4 mL |
| Viral characterization | 1 | 1 x 4 mL | None | 4 mL |
| Vitamin B12 | 1 | 1 x 2 mL | None | 2 mL |
| Serum pregnancy test | 1 | 1 x 2 mL | None | 2 mL |
| Tuberculosis (interferon-gamma release assays) | 1 | 1 x 3 mL | None | 3 mL |
| Sample for immune status | 8 | 1 x 4 mL | 7 x 4 mL | 32 mL |
| PD sample | 9 | 1 x 4 mL | 8 x 4 mL | 36 mL |
| PK analysis | 7 | 1 x 3 mL | 6 x 6 mL | 39 mL |
| Pharmacogenetic sample | 1 | 1 x 3 mL | None | 3 mL |
| All blood samples, total volume whole blood collected | | 80 mL | 322 mL | 402 mL |
| CSF | | | | |
| PD and PK samples | 3 | 1 x 12 mL | 2 x 12 mL | 36 mL |

CSF = cerebrospinal fluid, Ig = immunoglobulin, INR = International Normalized Ratio, PBMC = peripheral blood mononuclear cell, PD = pharmacodynamics, PK = pharmacokinetic, PT = prothrombin time, PTT = partial thromboplastin time.

